Title	A virtual cohort to measure monkeypox vaccine uptake and efficacy in Australia
Short title	TraX: Tracking our communities' responses to the monkeypox (MPX) outbreak.
Rationale and aim	In the context of the monkeypox virus (MPX) health emergency, New South Wales Health and the Department of Health Victoria have commenced vaccinating high-risk gay, bisexual, and other and other males or non-binary people who have sex with cis or trans men (GBMSM+) with an unlicensed third generation smallpox vaccination under the Therapeutic Goods Administration (TGA) emergency use authorisation.
	The recommended approach is two doses administered subcutaneously, a minimum of 28 days apart. This approach has equivalent immunogenicity to an older smallpox vaccine, but as it has not previously been used to prevent clinical monkeypox, the degree of clinical efficacy is uncertain. In the context of a global vaccine shortage, and consistent with advice from the Australian Technical Advisory Group on Immunisation (ATAGI), the New South Wales (NSW) and Victorian governments will use a dose sparing approach in some recipients. This will involve administration of a 1/5 th reduced dose intra-dermal (ID) administration of MPX vaccines rather than the standard dose administered subcutaneously.
	While one high quality clinical study has demonstrated non- inferior immunogenicity of the ID regimen, the degree to which the dose-reduced regimen will prevent clinical disease is uncertain. This project will investigate MPX vaccine uptake and real-world effectiveness in Australia.
Primary objectives	 Determine the baseline prevalence of past MPX infection and the prospective incidence of MPX over 12 to 18 months of follow-up. Determine vaccine effectiveness, adjusted for risk behaviour, measured separately for subcutaneous and intra-dermal routes, and separately for pre-exposure and post-exposure vaccination, and by time since vaccination. Measure vaccine uptake and determine predictors of vaccine uptake.

Secondary objectives	 Measure predictors and severity of breakthrough infections after vaccination. Identify under-vaccinated sub-populations to enable public health response.
Inclusion criteria	 Age 18 years or older. All people (whether cis or trans men, cis or trans women, or non-binary) who Report sex with cis and trans gay, bisexual, and other males or non-binary people who have sex with cis or trans men (GBMSM+) in the preceding 12 months. Currently living in Australia.
Recruitment	Community-recruited sample through online platforms, community organisations, and sector partners including Health Departments, including at clinics at which vaccination occurs.
Number of planned participants	 Sample size for the estimation of monthly incidence of vaccine coverage: 2,000. Sample size for the estimation of vaccine efficacy over 12 months of follow-up: 14,949 (3,000 initially unvaccinated and 12,000 initially vaccinated).
Study design	Entirely online, self-directed, self-report prospective observational study.
	Our study is an entirely online self-report observational study of a vaccine uptake and effectiveness. The study team is not involved in the vaccination intervention which is being implemented by state and territory health departments as part of the response to the MPX public health emergency.
Study procedures	This study is an online cohort study and eligibility assessment, consent, and survey completion is entirely self-directed and automated through our data collection system.
	Following consent and enrolment, we will collect data relevant to the research objectives (monkeypox diagnosis and severity, vaccination, risk behaviour) each week for a minimum of 52-weeks and up to 78 weeks depending on date of recruitment. In addition to very brief (< 3 minute) weekly questionnaires, there will be slightly more detailed questionnaires at baseline, 6 and 12 months, and exit survey. Follow-up continues until the last enrolled participant has been followed for 52-weeks.
Study duration	Eighteen months, comprising 6 months of open recruitment and a minimum of 52-weeks of follow-up per participant.

Schedule of assessment

Items	Baseline	Weekly	Six- monthly	Optional one-off modules
Informed consents	Х			
Optional consent	Х			
Demographics	Х			
MPX vaccination	Х	Х	Х	
MPX vaccination tolerability and side effects				Х
MPX testing	Х	Х	Х	
MPX positive diagnosis module				Х
Experience of MPX diagnosis				Х
Sexual behaviours	Х	Х	Х	
COVID-19 infection history	Х			
HIV and STI testing	Х		Х	
ARV use	Х		Х	

Study timeline

		20	22			2023								2024							
	September	October	November	December	January	February	March	April	May	June	ylut	August	September	October	November	December	January	February	March	April	May
Steering committee	٠	•	•	•		•			•			•			٠			•			•
Funding	•	•																			
Ethics approval	•																				
Enrolment	•	•	•	•	•	•	•														
Data collection	•	•	•	•	•	•	•	•	•	•	•	•	•	•	•	•	•	•	•		

PrEP PRSP STI TGA	Pre-exposure prophylaxisPrevention Research Support ProgramSexually transmissible infectionsTherapeutic Goods Administration
PrEP PRSP STI TGA TraX	Pre-exposure prophylaxisPrevention Research Support ProgramSexually transmissible infectionsTherapeutic Goods AdministrationTracking the community response to monkeypox
PrEP PRSP STI TGA TraX US	Pre-exposure prophylaxisPrevention Research Support ProgramSexually transmissible infectionsTherapeutic Goods AdministrationTracking the community response to monkeypoxUnited States

1 BACKGROUND AND RATIONALE

1.1 BACKGROUND

Since early May 2022, more than 40,000 cases of monkeypox virus (MPX) have been identified globally in non-endemic countries.^{1,2} On July 23 2022, the World Health Organization Director declared the monkeypox outbreak a Public Health Emergency of International Concern.³ Cis gay, bisexual, and other men who have sex with men (GBM) account for more than 95% of cases.^{4,5} Cases have also been described in trans men and women, mostly due to sexual contact with GBM, and it is anticipated that cases will also emerge in cisgender women who have sex with GBM. Transmission is through close skin-to-skin contact with someone who is MPX-positive. Some evidence suggests MPX can also be spread through large respiratory droplets or contaminated surfaces,^{1,2} and the presence of live virus suggests it may also be transmitted in semen.⁶ The current outbreak initially occurred in highly sexually active men who attended large Pride events and sex parties in North America and Europe, and observational data overwhelmingly suggest sexual transmission with no airborne transmission and very limited household transmission.^{1,7}

Globally, the public health response to MPX has primarily focused on the rapid and targeted rollout of the third-generation smallpox vaccine based on modified vaccinia Ankara manufactured by Bavarian Nordic (MVA-BN, Australian trade name JYNNEOS®) to those most at risk of MPX infection. MVA-BN was licensed for smallpox prevention in the United States and Europe based on the fact that in vaccine-naïve individuals it produces geometric mean titres (GMT) of vaccinia-specific antibody which are non-inferior to those produced by the second-generation smallpox live-virus vaccine ACAM2000. MVA-BN is based on a highly attenuated strain of vaccinia which is replication incompetent in humans, meaning it is safe to be used in immune deficient populations. The vaccine is recommended to be administered as two 0.5 ml doses, administered subcutaneously, separated by at least 28 days. The United States Food and Drug Administration (FDA) also granted a monkeypox prevention indication. This was based on the fact that variola, vaccinia and monkeypox viruses are orthopoxviruses belonging to the poxviridae family and vaccinia-based vaccines induce cross protection for orthopoxviruses, and evidence from non-human primates that MVA-BN protects against lethal monkeypox challenge. Thus, the evidence for protection against clinical monkeypox in human remains somewhat uncertain because clinical studies have not been performed in humans prior to the current epidemic. A study in 1988 estimated 85% protection of first generation smallpox vaccines against monkeypox, but was done at a time when residual immunity from exposure to natural smallpox and from vaccination was high.⁸ Forty years after smallpox eradication, we estimate virtually no residual immunity to vaccinia in New South Wales (NSW) and only 10% of the population being ever-vaccinated.^{9,10} MVA -BN is not yet registered by the Therapeutic Goods Administration (TGA), but it is being used in Australia under an exemption provided by section 18A of the Therapeutic Goods Act 1989, which ensures that vaccines are available urgently to address public health threats.¹¹

With limited doses of MVA-BN available, current estimates suggest that vaccine demand in Australia and elsewhere will far exceed supply, and it is uncertain what proportion of those at risk will be covered by existing supplies. Given the lack of vaccine supply, GBM most at risk of MPX infection have been prioritised.¹¹

In the global context of demand exceeding supply, vaccine dose-sparing approaches which may allow more people to be vaccinated have been discussed including two main approaches. The first is giving one dose only, or by substantially delaying the second dose. However, one dose has inferior immunogenicity to two doses, and there are thus concerns it may be less clinically effective. The second approach is administering a one-fifth dose (0.1ml rather than 0.5ml) intradermally rather than subcutaneously, with the standard minimum 28 days spacing. The intra-dermal route has historically been used as a means to enhance the immunogenicity of rabies, inactivated polio and influenza vaccines.¹²⁻¹⁵ The only study of the immune response to this regimen for MVA-BN demonstrated that the reduced dose administered intra-dermally resulted in non-inferior immunogenicity to MVA-BN administered subcutaneously. Based on this result, on 9 August 2022, the US FDA issued an emergency use authorisation allowing two doses of the reduced intra-dermal dose.¹⁶ US authorities have commenced use of the reduced-dose intra-dermal regimen, thus allowing five times as many men to be vaccinated with a regimen that has equivalent immunogenicity to the subcutaneous administration of the standard dose. On 26 August 2022, Australia's technical advisory group on immunisation released advice which also allowed intra-dermal administration.¹⁷

With limited vaccine availability in a public health emergency, and an urgent need to administer doses to as many GBM as possible, current advice on the best dosing strategies is rapidly evolving. In the context of the MPX health emergency, New South Wales Health and the Department of Health Victoria have started using reduced dose intra-dermal administration of MVA-BN to GBM at risk of MPX. While one high quality clinical study has demonstrated non-inferior immunogenicity, the degree to which the two-dose intra-dermal regimen will prevent clinical disease is unknown. The World Health Organization's guidance on monkeypox vaccination recommends that vaccination should occur in a research framework, and that observational approaches to assess vaccine efficacy should be carefully designed to minimise bias.¹⁸

1.2 RATIONALE

Data are required to address two key public health issues:

1.2.1 VACCINE COVERAGE

In the setting of insufficient vaccine supply, and a population for which there is no accurate denominator estimate, regular timely measures of the proportion of those at risk who have been vaccinated are required to inform public health action to guide vaccine roll-out.

1.2.2 VACCINE EFFICACY

As outlined above, there is no direct clinical evidence that MVA-BN prevents clinical monkeypox in humans. By following a cohort of participants who receive vaccination as part of the public health response over a period of some months, we will be able to examine vaccine efficacy, defined as the incidence of disease among the vaccinated divided by the incidence of the disease in the unvaccinated. By collecting information on the date of vaccination, number of doses received, timing of receipt of vaccine if administered post high-risk exposure, and route of receipt (subcutaneous or intradermal), we will be able to calculate vaccine efficacy by number of doses, time since vaccination, and by route of vaccination. It is likely vaccine uptake will be associated with high-risk behaviour, so it will be critical that we collect regular information on risk behaviour to allow vaccine efficacy in those with MPX to see if cases in the vaccinated are less severe than in the unvaccinated. In this international public health emergency, it is critical that we commence data collection as soon as possible, to allow estimates of disease in the unvaccinated, and to describe the rate of vaccine uptake in those at risk.

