2.2 PRIMARY OBJECTIVES

- 1. Determine the baseline prevalence of past MPX infection and the prospective incidence of MPX over 12 to 18 months of follow-up.
- 2. Determine vaccine effectiveness, adjusted for risk behaviour, measured separately for subcutaneous and intra-dermal routes, and separately for pre-exposure and post-exposure vaccination, and by time since vaccination.
- 3. Measure vaccine uptake and determine predictors of vaccine uptake.

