3 STUDY DESIGN

3.1 SUMMARY OF STUDY DESIGN

To address the study objectives, this project will rapidly initiate an entirely online prospective observational study that will systematically survey participants each week for a minimum of 52 and up to 78 weeks to measure the short-term impacts of MPX and to detect trends throughout the MPX epidemic. Enrolment will occur for the first 6 months of the study period. If the epidemic is ongoing after 18 months, further follow-up may be considered. Participants will not be reimbursed for their participation, nor will their participation incur any expenses.

We will systematically follow individual participants each week for up to 18 months (12 months for those participants recruited at the end of month six). The weekly surveys will include questions on MPX testing, vaccination, and diagnosis, while also asking about sexual behaviours, including use of condoms and sexual positioning to determine any associations with the site of MPX infection. Each week, participants who indicate they have had a vaccination or positive diagnosis will answer additional questions, including severity of symptoms and location of infection.

Through the community-recruited sample, we will be able to identify uptake of MPX vaccines by age, sexual risk behaviours, and geographical coordinates (postcode). These data will allow us to identify subpopulations of under-vaccinated communities to inform targeted public health campaigns.

In consenting participants, data linkage will validate self-reported MPX infection and any significant adverse events to MPX infection and vaccination. Consent to data linkage is an optional component to the study.

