6.5 WEEKLY QUESTIONNAIRE

The weekly questionnaire will take approximately 1 minute to complete depending on individual responses to items on sexual behaviour. Weekly questionnaire items include MPX testing, vaccination, diagnosis, and sexual behaviours.^{2,6,34-36}

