9.2.1 PRIMARY OUTCOME MEASURES

- 1. MPX Incidence per 100 person years of MPX
- 2. Vaccine effectiveness, adjusted for risk behaviour, measured separately for subcutaneous and intra-dermal routes, and separately for pre-exposure and post-exposure vaccination.
- 3. Vaccination Incidence per 100 person years, and predictors of vaccine uptake.

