9.3.2 VACCINE EFFICACY

- Disease incidence: Number of events observed (new MPXV infections) divided by total person years followed, presented as cases per 100 person-years.
- Vaccine efficacy: (incidence in unvaccinated incidence in vaccinated, divided by incidence unvaccinated)
- Multivariate: controlled for behaviour using Cox regression.

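### Post-exposure effectiveness is a primary outcome, but the protocol names no exposed-unvaccinated comparator and lists no exposure item for unvaccinated participants, so the estimate is not identifiable as planned and is likely biased against the vaccine

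*Protocol*

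**What the plan says.** - **Status of the estimate.** Section 2.2 asks for effectiveness "separately for pre-exposure and post-exposure vaccination, and by time since vaccination". Sections 5.1 and 9.2.1 repeat the split as a primary endpoint and a primary outcome measure ("separately for pre-exposure and post-exposure vaccination").
- **Comparator.** Section 9.3.2 gives one formula, "incidence in unvaccinated incidence in vaccinated, divided by incidence unvaccinated", read here as the difference in incidence over the incidence in the unvaccinated. Section 1.2.2 gives the plain ratio of the same two incidences. Neither limits the unvaccinated group to people with an exposure.
- **Adjustment.** Section 9.3.2 adds "Multivariate: controlled for behaviour using Cox regression". Section 9.3 mentions longitudinal models with time-varying exposures and leaves detail to a Statistical Analysis Plan, which is not shown.
- **Where exposure is recorded.** Section 1.2.2 lists, among the details of a vaccination, "timing of receipt of vaccine if administered post high-risk exposure".
- **What everyone is asked.** Section 6.5: "Weekly questionnaire items include MPX testing, vaccination, diagnosis, and sexual behaviours". Section 3.1 gives the same list and adds condom use and sexual positioning. The schedule of assessment and sections 6.4, 6.6 and 6.7 add demographics, vaccine attitudes, HIV and STI items, antiretroviral use, and symptoms and severity after a diagnosis. None of these lists names contact with a case or an exposure date.

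**The concern.** A person vaccinated after exposure is, by definition, at raised short-term risk when the vaccine is given. A fair comparator is someone with a similar exposure who was not vaccinated. The protocol does not name that group, and none of its listed items would identify it. With the general unvaccinated group as comparator, the risk carried by the exposure is counted against the vaccine.

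Condom use, positioning and similar items describe general risk. They do not show whether a given partner had MPX. A later analysis plan can choose the risk set and the time origin, but it cannot supply exposure dates that were never asked for. At stake is one stratum of a primary outcome, which could understate protection or show apparent harm from a protective vaccine. The first weeks are the most affected, and effectiveness by time since vaccination is part of the same primary objective.

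**Working it through.** **1. The plan's own figure (section 9.1.2).** Inputs: effectiveness 70% (HR 0.30), 1 per 100 person-years in the unvaccinated, 20% initially unvaccinated, 80% of these vaccinated within 12 months, 80% power, two-sided alpha 0.05.

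- Unvaccinated share of the year in the initially unvaccinated, with constant-hazard crossover: 0.8 / -ln(0.2) = 0.497.
- Their hazard relative to no vaccination: 0.497 + 0.503 × 0.30 = 0.648. Diluted HR: 0.30 / 0.648 = 0.463.
- Freedman events at 1:4: (1.960 + 0.842)² × (1 + 4 × 0.463)² / [4 × (1 - 0.463)²] = 55.3, rounded up to 56.
- N = 55.3 / average event probability = 15,007.

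The protocol states 56 events and 14,949 participants, so the figure reproduces within 0.4% and is not in dispute. It covers vaccinated versus unvaccinated overall, not the post-exposure stratum.

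**2. Unadjusted bias with the general comparator.** From the protocol: background rate 0.01 per person-year and true effectiveness 70%. Assumed, because the protocol gives neither: a 21-day risk window (w = 21/365 = 0.0575 year) and an attack risk s after exposure without vaccine.

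- Background risk over 21 days: 0.01 × 0.0575 = 0.058%.
- HR over 21 days = -ln(1 - 0.3s) / (0.01 × w).
- HR over 52 weeks = [-ln(1 - 0.3s) + 0.003 × (1 - w)] / 0.01.
- Apparent effectiveness = 1 - HR.

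| Attack risk s | HR, 21 days | Apparent, 21 days | HR, 52 weeks | Apparent, 52 weeks |
|---|---|---|---|---|
| 0.5% | 2.6 | -161% | 0.43 | 57% |
| 1% | 5.2 | -422% | 0.58 | 42% |
| 2% | 10.5 | -946% | 0.88 | 12% |
| 5% | 26.3 | -2,527% | 1.79 | -79% |
| 10% | 52.9 | -5,194% | 3.33 | -233% |

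Apparent effectiveness reaches zero when 0.3s equals 0.000575 (21 days), so s = 0.19%, or when 0.3s equals 0.01 - 0.00283 = 0.00717 (52 weeks), so s = 2.4%.

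**3. Forces that reduce the bias.**

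- *Behaviour adjustment.* If it removed a tenfold difference in risk, the 21-day HR would be divided by 10. Apparent effectiveness becomes 74% at s = 0.5%, 48% at 1%, -5% at 2% and -163% at 5%.
- *Diagnosis before vaccination.* Exposed people diagnosed before they are vaccinated never enter the post-exposure group. If this removes a share g of would-be cases, the 52-week HR is about [0.3s(1 - g) + 0.00283] / 0.01. At s = 5% it falls from 1.78 (g = 0) to 1.33 (g = 0.3) and 0.88 (g = 0.6), against a true 0.30.

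**4. Comparison within the exposed.** With the same attack risk in both groups, HR = 0.3s / s = 0.30 and the assumed 70% is recovered. For 80% power, two-sided 0.05 and 1:1 allocation, this needs 2,068 exposed people per arm at s = 1%, 1,027 at 2%, 402 at 5% and 194 at 10%. That is about 20 unvaccinated exposed cases in each setting (for example 402 × 0.05 = 20.1). Under step 1, all unvaccinated person-time yields about 2,990 × 0.497 × 0.01 = 14.9 cases in 12 months, and not all of these would have a recognised exposure. A precise estimate is therefore unlikely at the planned size.

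**The case against.** The strongest reply is that the protocol does not say what a reader might infer from it.

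- *A reader might infer that exposure is recorded only in the vaccinated.* The protocol lists topics, not questions, and the questionnaires are not shown. An exposure question could sit under testing or sexual behaviours. This stands: the gap is in the listed items and must be checked against the questionnaire.
- *A reader might infer that high-risk exposure means known contact with a case.* The protocol leaves the term undefined. If it includes high-risk sex, the weekly behaviour items capture part of it in everyone. This stands, and it is why a definition comes first in the remedy.
- *A reader might infer a commitment to compare post-exposure recipients with all unvaccinated person-time.* Section 9.3.2 is a general formula, the primary estimate is adjusted for risk behaviour, and the analysis plan may set a different risk set. This stands in part. The analysis plan can restrict to the exposed only if exposure was recorded in the unvaccinated.
- *The estimate need not be negative.* At an attack risk of 0.5% to 1% the 52-week figure stays positive without adjustment, and both forces in step 3 pull it upwards. This stands.

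The sample size, incidence and uptake objectives do not depend on this stratum.

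**Conclusion.** The point holds in a limited form. The protocol gives a primary post-exposure estimate no exposed-unvaccinated comparator and lists no item that would identify one. As planned, the estimate is not identifiable against that group and is likely biased against the vaccine.

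The documents do not support saying that the result will be strongly negative. The size rests on an assumed attack risk and a 21-day window, with 70% effectiveness and 1 per 100 person-years taken from section 9.1.2. Unadjusted 52-week apparent effectiveness runs from 57% at an attack risk of 0.5% to -233% at 10% and changes sign at about 2.4%. In the first three weeks the unadjusted figure is negative above 0.19%. Adjustment and diagnosis before vaccination lessen the bias by an amount that cannot be known from the protocol.

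This should be fixed, but it does not threaten the study as a whole: it concerns one stratum of one of three primary outcomes.

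**What to change.** 1. Define post-exposure vaccination for the analysis, including what counts as an exposure.
2. Check the weekly questionnaire. Unless it already does so, ask every participant, vaccinated or not, about known contact with or exposure to a person with MPX since the last survey, with the date.
3. Estimate post-exposure effectiveness only among participants reporting an exposure. Start follow-up at the exposure date and treat vaccination as a time-varying covariate, so that cases before vaccination count as unvaccinated.
4. If exposed-unvaccinated numbers prove too small, report this stratum descriptively and remove it from the primary estimates in sections 2.2, 5.1 and 9.2.1.

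The cost is a few seconds per weekly survey, an ethics modification and, by step 4 of the working, an estimate that will probably be imprecise. An early change matters because exposure dates not asked for weekly would later depend on recall.
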